**10. Payment and Remuneration**

a. Detail compensation for participants including possible total compensation, proposed bonus, and any proposed reductions or penalties for not completing the protocol.

Participants will be paid \$30 for completing the Screening visit. Enrolled participants will earn \$50 for each session day and will incur a completion bonus that will escalate in value with each subsequent session. Bonuses will be earned for completion of the study only and any participant who ends the study prematurely will receive their session payments but will forfeit the completion bonus. Participants can earn up to \$750 in payments and bonuses for study participation.

Study Day	Session Payment	Completion Bonus	
Admission	\$50.00	\$50.00	
Day 2	\$50.00	\$75.00	
Day 3	\$50.00	\$100.00	
Day 4	\$50.00	\$125.00	
Day 5	\$50.00	\$150.00	
Total:	\$250.00	\$500.00	\$750.00

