Participants are healthy controls. They are not treatment-seeking and do not have any underlying medical condition that would warrant continued treatment upon completing the study. Participants will be informed they can agree to begin the study now and withdraw later without any penalty. Participants who request to discharge from the study prior to completing the study will be assisted with contacting medical professionals upon request from the participant.

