We have chosen to deliver doses lower than those administered by that study so we may evaluate whether there are individual differences in the ability to detect the low dose of hydromorphone. Participants in our study will receive three active hydromorphone doses. The first dose participants will receive is the mid-level dose, which will be administered on study Day 2. Any participant who has a negative reaction to this dose will be discharged from the study. The participants will receive placebo, low, and high doses on Days 3-5 of the study; the order of doses will be randomized and counter-balanced. These doses were deemed safe in the same participant population in the Walsh study, they produced a documented detectable range of subjective effects, and they represent suprathreshold doses consistent with those abused recreationally. Ultimately, we feel confident these dose values do not impose any unique risk above and beyond that presented by the administration of hydromorphone.

Generic powdered hydromorphone will be encapsulated using size 0, opaque, hard gelatin capsules; placebo will be size and weight matched and will contain microcrystalline cellulose filler. A pharmacy member with no participant interaction will conduct the dose randomization. All medication administration will be supervised and a medical staff member will be available to address any adverse events or to break the medication blind.

- b. Justification and safety information if FDA approved drugs will be administered for non-FDA approved indications or if doses or routes of administration or participant populations are changed.

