## 7. Study Statistics

a. Primary outcome variables. The primary outcome variables are self-reported ratings of drug high and liking, changes in pupil diameter and blood pressure, pain threshold on 2 laboratory measures of pain, and analgesic efficacy in response to laboratory-induced pain. We expect that individuals with the minor allele of the A118G SNP and other

tagging SNPs across the OPRM1 gene will find hydromorphone more reinforcing (e.g., higher self-report ratings of high and drug-liking) and exhibit greater opioid-induced physiological changes (e.g., pupil diameter, blood pressure). Research also suggests the OPRM1 gene may also confer greater sensitivity to the negative effects of opioids, which may be observed as measuring greater ratings of nausea. We also hypothesize the minor allele and other tagging SNPs across the OPRM1 gene will produce higher pain threshold on 2 laboratory measures of pain, and lower analgesic efficacy in response to laboratory induced pain.

**b. Secondary outcome variables.** Decreases in cortisol levels as a function of the degree of pleasant effects of hydromorphone and painful stimuli, delay-discounting curves, and the effect of sex on all outcome measures. We hypothesize that individuals with the minor alleles will have greater decreases in cortisol levels as a function of the degree of pleasant effects of hydromorphone, lower cortisol in response to painful stimuli, and steeper discounting curves on a delay-discounting task. Finally, although we expect that the A118G will be associated with these effects, we hypothesize that several of the additional OPRM1 tagging SNPs will contribute to effect magnitude.

**c. Statistical plan including sample size justification and interim data analysis:** The aims of the proposed study will explore the impact of genetic variation across the OPRM1 gene on hydromorphone response. There are specific steps we describe below to assure that we interrogate all known functional variation across the OPRM1 gene, adequately cover all other variation using appropriately selected tagging SNPs, prevent spurious associations due to population stratification by accounting for local ancestry, and properly control the Type I error rate.

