Protection Against Hydromorphone Risks: We also have extensive experience in the administration of hydromorphone and other opioid agonists in controlled laboratory settings and therefore anticipate few problems. Any individual who may be prone to the risks associated with hydromorphone will be excluded from participating. The FDA has identified the following conditions as increasing the risk for respiratory depression or other serious side effects following hydromorphone administration: patients with status asthmaticus; chronic obstructive pulmonary disease; reduced respiratory function; high blood pressure; impairment of hepatic, pulmonary or renal functions; myxedema or hyperthyroidism; adrenocortical insufficiency; gall bladder disease; acute alcoholism; history of convulsive disorders; history of head injury; currently taking sedatives, hypnotics or phenothiazines; and sulfite allergy. Mean exposure to hydromorphone is also increased 4-fold among patients with hepatic impairment and 3-fold among patients with renal impairment. Therefore, to further reduce the risk serious side effects, we will exclude any potential participant who exhibits one or more of these conditions. Second, although research staff and participants will be blinded to the exact medication provided, both groups will be informed of the potential side effects and risks associated with the study drug administration. Third, participants will be free to discontinue study participation at any time without consequence. Great care has been taken in selecting the appropriate drug doses to ensure hydromorphone is well-tolerated and safe for our participants. Fourth, standard concomitant medications (e.g., anti-nausea medications) will also be available as needed to treat any unpleasant side effects that may occur as a result of hydromorphone administration and participants will also be able to discontinue study participation at any time. Finally, the most serious risk associated with hydromorphone administration is respiratory depression. We believe this risk is minimal in this study for several reasons. First, we have selected a range of equipotent doses that we have previously demonstrated to be safe and well-tolerated in the same participant population (non opioid dependent individuals) (99-102) and based upon a previous study that piloted and ultimately administered identical doses to an identical research sample (136). Second, we have developed several standard criteria that are followed by nursing staff and research personnel to monitor participants who have been provided with a study medication. All nursing and research staff are informed of these standards, and a list of these standards is posted in each testing room. The standards are as follows: If respiratory rate drops below 8 breaths/minute and is accompanied by sedation, participants are prompted verbally to breath. In our experience, verbal and physical stimulation is often sufficient to prompt breathing and restore a normal respiratory rate. If respiratory rate drops further and/or if oxygen saturation rates fall below 90% saturation, successive dosing is terminated. Patients are monitored carefully with a “watch and wait” approach; during this period they are accompanied continuously by a medical and/or nursing staff member, evaluated by a staff physician, and are given supplemental oxygen at 2L/min via a nasal cannula (available on site in the exam testing room). If clinical evaluation determines that a participant’s sedation level is increasing, the opioid antagonist naloxone can be promptly administered via intramuscular route to produce an immediate reversal of opioid effects. There have been very few incidents throughout our >15 year experience administering opioid agonists to human participants in controlled laboratory conditions that have necessitated actual intervention (oxygen and/or naloxone), however our equipment and medical/nursing staff is always prepared for this possibility. We feel these procedures will sufficiently protect participants from possible adverse and serious adverse events. Finally, we will submit an annual review of study-related adverse and serious adverse events to the Johns Hopkins IRB and an independent group of consultants who will serve as our data safety monitoring board for evaluation.

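### The $500 completion bonus (67% of in-study pay) has no exception for safety discharge, and its forfeiture conflicts with the stated freedom to stop

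*Combined protocol and SAP*

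**What the plan says.** Section 10a pays $50 for each of five days (Admission and Days 2 to 5). Participants also "will incur a completion bonus that will escalate in value with each subsequent session": $50, $75, $100, $125 and $150. The condition is strict: "Bonuses will be earned for completion of the study only". For people who leave early, section 10a spells out the result: "any participant who ends the study prematurely will receive their session payments but will forfeit the completion bonus". No exception for adverse events, medical reasons or investigator decisions appears there or elsewhere in the document.

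Two other sections describe leaving early as free of cost. Section 4g says participants will be told that they may start and "withdraw later without any penalty". Section 8b, among its protections against hydromorphone risk, says that "participants will be free to discontinue study participation at any time without consequence".

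Several sections have staff end participation. Section 6a, on the mid-level dose given on Day 2, says: "Any participant who has a negative reaction to this dose will be discharged from the study". Section 7d discontinues anyone with a serious side effect that seems drug-related and allows medical discharge for intercurrent illness. Section 4f removes participants for allergic reaction. Table 1, exclusion 8, gives a narrower first-dose trigger: an adverse event that calls for an opioid antagonist.

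**The concern.** There are two problems.

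The first is consistency. Losing two thirds of the available pay is a consequence of stopping, whatever one calls it, so sections 8b and 10a cannot both be accurate as written. The prompt for section 10a itself asks for reductions or penalties for non-completion, and the forfeiture is part of the answer given.

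The second is incentive. Section 6a uses the Day 2 dose as a tolerability check. Placebo, low and high doses follow on Days 3 to 5 in randomised order. If a disclosed reaction leads to discharge and discharge forfeits the bonus, a participant with a tolerable but unpleasant reaction has a financial reason to say nothing and go on to the remaining doses. Adverse-event reports and subjective responses also feed the mid-point review in section 7d, so full disclosure matters for oversight as well as for the individual.

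**Working it through.** **Inputs** (section 10a table): session pay $50 × 5; bonus schedule $50, $75, $100, $125, $150; stated maximum $750. The $30 screening payment is outside the $750.

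**Reproducing the plan's total.** Sessions: 5 × 50 = $250. Bonus: 50 + 75 + 100 + 125 + 150 = $500. Sum: 250 + 500 = $750, which matches.

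**Bonus share.** 500 / 750 = 66.7%. With the screening payment in the denominator, 500 / 780 = 64.1%.

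**Pay by last day attended**, assuming that the day of exit counts as a paid session day:

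| Last day | Session pay kept | Bonus scheduled to that day | Shortfall against a completer, current rule | Total if scheduled bonus is paid |
|---|---|---|---|---|
| Admission | $50 | $50 | $700 (93.3%) | $100 |
| Day 2 | $100 | $125 | $650 (86.7%) | $225 |
| Day 3 | $150 | $225 | $600 (80.0%) | $375 |
| Day 4 | $200 | $350 | $550 (73.3%) | $550 |
| Day 5, not completed | $250 | $500 | $500 (66.7%) | $750 |

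**What the Day 2 shortfall contains.** Of the $650, session pay for the three days not attended is 3 × 50 = $150. Bonus scheduled for those days is 100 + 125 + 150 = $375. Bonus scheduled for the two days attended is 50 + 75 = $125. Check: 150 + 375 + 125 = $650. Only the $125 relates to days the participant actually completed.

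**Does the rule reach safety discharge?** Section 10a does not name it. Three features point that way: the bonus depends on completion alone, the forfeiture sentence covers any participant, and no exception is stated. Against this, the forfeiture sentence speaks of a participant who ends the study, whereas sections 4f, 6a and 7d describe staff-initiated exit as being removed, discharged or discontinued. The first reading is the more natural one, but the text does not settle it.

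**Who would be discharged after the first dose?** The section 6a trigger is undefined and could be broad. The trigger in Table 1, exclusion 8, is a specific clinical threshold. The number of people affected depends on which applies.

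**The case against.** The strongest reply is that the incentive argument reaches too far, and much of that reply stands.

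- A reader might infer that any honest report of nausea or dizziness ends participation. The documents do not support this. Exclusion 8 sets a higher bar, section 8b provides anti-nausea medication for unpleasant effects, and the later triggers in sections 4f, 7d and 8b are allergic reactions, serious side effects, and respiratory rate or oxygen saturation. Ordinary ratings of nausea or bad effects trigger none of these.
- A reader might infer that adverse events are known mainly through self-report. The documents do not say so. Sessions include observer ratings, vital signs, oxygen saturation and pupillometry, and staff monitor participants around the clock.
- A reader might infer bias in the genotype comparison, because section 7a suggests that the gene may "confer greater sensitivity to the negative effects of opioids, which may be observed as measuring greater ratings of nausea". That is not shown. Nausea is not among the listed primary outcome variables, participants are not told their genotype, and nothing in the documents indicates that under-reporting would differ by genotype.
- It would be wrong to call the forfeited money earned. Under section 10a nothing is earned before completion, so the accurate term is scheduled bonus.
- Section 8b also says that consent to pain testing may be revoked without penalty. Section 10a does not say that doing so forfeits the bonus, so no direct conflict is shown there.

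The consent pages are not available for this review, so an exception stated there cannot be ruled out. The forfeiture is also openly disclosed in the section meant for it.

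None of this reconciles section 10a with section 8b, and none of it supplies a rule for medical discharge.

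**Conclusion.** The point holds as a modest consistency and participant-protection issue. The $500 bonus is 66.7% of in-study pay. As written, a staff-initiated safety or medical discharge appears to forfeit all of it, leaving $100 after a Day 2 discharge. This conflicts with section 8b and sits poorly with section 4g, where one can argue that an unearned bonus is not a penalty.

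The reason not to disclose a reaction is an inference from the payment and discharge rules taken together. It assumes that participants know, or come to believe, that a reported reaction may lead to discharge. Its effect on reporting cannot be estimated from the documents. The claim that safety discharge is covered rests on general wording and a missing exception, not on an explicit statement. No endpoint, sample size or analysis is affected.

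**What to change.** 1. In section 10a, state that a participant discharged by staff for a safety or medical reason receives session pay plus the scheduled bonus amounts through the last day attended: $125 on Day 2, $225 on Day 3, $350 on Day 4 and up to $500 on Day 5.
2. Reword sections 4g and 8b, and the consent form if it uses the same language, to disclose that voluntary early exit forfeits the bonus. The change to section 10a does not resolve that conflict, because forfeiture for voluntary exit stays.
3. Reconcile the first-dose discharge triggers in section 6a and Table 1, exclusion 8, so that it is clear whom the payment rule covers. Which trigger applies is for the investigators to decide.

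The cost is protocol and consent wording plus $125 to $500 per safety discharge after dosing begins. The documents give no expected number of discharges; if ten on Day 2 are assumed for scale, 10 × 125 = $1,250. The retention incentive weakens slightly. The change narrows the financial reason to stay silent but does not remove it: the Day 2 shortfall falls from $650 to 750 − 225 = $525, all of it pay for days not attended.

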**11. Costs**

a. Detail costs of study procedure(s) or drug (s) or substance(s) to participants and identify who will pay for them.

All study procedures and study drug will be supported by a grant from the National Institute on Drug Abuse and will be provided to participants free of charge.

